Measures. The primary outcomes will include changes in the D5 measures (A1C <8%, blood pressure <140/90 mmHg, not using tobacco, taking a statin and aspirin use as appropriate). These measures will be ascertained at baseline and 12 months after study enrollment. Interim D5 measures and those unavailable at follow-up will be extracted from Hutchinson Health and NUMC's EHR where possible. Secondary outcomes will include nutrition, physical activity, body mass index, medication adherence, confidence and satisfaction with diabetes management and gender. Specifically:

- Height
- Weight
- Waist Circumference
- Blood pressure
- Labs: A1c, fasting glucose, lipids
- Lifestyle questionnaire (see attachments)

Phone coaching

Phone visits will occur monthly over the course of one year, with some variability as needed such as more frequent phone contacts when a medication is started. They will be conducted by study coaches and last approximately 30 minutes. Topics will include:

- Brief lifestyle & medication assessment
- Nutrition coaching regarding appropriate choices (e.g. carbohydrate choices at meals/snacks, healthy fats, portion control).
- Physical activity recommendations
- If needed, medication initiation/titration for blood pressure, cholesterol or blood glucose

12-month/Final visit

The study follow-up visit will be similar to the baseline visit and occur at the Hutchinson Health clinic about 12 months later. The study follow-up visit will occur at NUMC for those patients identified from New Ulm. This will again be in-person and conducted by study coaches and lab personnel. The same measures will be taken as at baseline.

5. Study Procedures & intervention:

At the baseline visit, study participants will be randomized into the intervention or control group by computer using block randomization (block size 5).

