Coaches in this study will be registered dietitian/certified diabetes educators trained to address the D5 optimal care measures. They will also be trained in the use of a medication protocol that permits initiation and titration of blood glucose, lipid, and/or blood pressure medications (attachment). All coaching aside from the baseline and final visits is done via telephone and participants will generally receive a minimum of one call per month. The intervention is designed to complement to usual clinic-based primary care, with coaches documenting lab, biometrics, and medication adjustments in the EHR, along with documenting phone encounters and communicating directly with patients' PCPs as needed.

Documentation in the EHR uses an order created specifically for the study indicating the patient's research status; "opt-in" for those who choose to enroll.

To answer outcome evaluation questions, all individuals with a diabetes research study order will be extracted from the EHR along with baseline and 12 month D5 measures collected during respective visits. For comparisons between the intervention and usual care patients, the analysis

will examine mean changes in biometric risk factors and the percentage of patients meeting recommended levels for the D5 measures at baseline and after the one year intervention period. Medication changes will also be examined and compared between the two groups.

Study procedures will be approved in advance by the Allina Institutional Review Board.

Analysis

Analyses and power. A moderate effect size is expected of at least (Cohen's $w=0.25$) in this trial. Over one year, this translates into about 30% of the intervention group experiencing improvement in ≥ 1 D5 measure vs. 10% of usual care participants. Under the assumptions of 85% power, an alpha-level of 0.05, and a one degree of freedom test, 144 total participants (72 in each group) will be needed for this study. Mixed regression models will be used to compare D5 outcomes between the two study groups over time. Similar analyses will be conducted on secondary outcomes as well. An intent-to-treat framework will be used that will include all randomized participants.

6. Risk/ Safety information

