	Intention to improve lifestyle	Self-reported; single item indicating yes, maybe, or no intention to improve lifestyle habits over the next 6 months

	Confidence in managing diabetes	Self-reported; single item modified from Kettering Health Network and Joslin Diabetes Center Diabetes Self-Management Questionnaire ⁶ ; degree of confidence
	Satisfaction with diabetes care	Self-reported; single item; degree of satisfaction ⁷
	Social and emotional support	Self-reported; single item; frequency ⁷
General diabetes care (self-report survey)	Diabetes education	Self-reported; 3 items; last diabetes class ⁷ , last visit with diabetes nurse educator ⁸ , and last visit with dietitian ⁸
	Aspirin use	Self-reported; single item indicating daily aspirin or every other day use ⁹
	Medication adherence (statin, blood pressure, and diabetes)	Self-reported; 15 items; The MMAS ¹⁰ is a generic self-reported, medication-taking behavior scale in which the specific health issue (high blood pressure, diabetes, elevated cholesterol, HIV, contraception, etc.) is inserted for the “health concern.” The MMAS consists of four items with a scoring scheme of “Yes” = 0 and “No” = 1. The items are summed to give a range of scores from 0 to 4.
	Blood glucose monitoring	Self-reported; 2 items; frequency ^{4,7}
	Hypoglycemia	Self-reported; single item; frequency ¹¹
Anthropometrics (staff measured)	Blood pressure	Staff measured; participants sit for 5 min prior to 3 pressures taken 1 min apart using auto sphygmomanometers (mean of last 2 measures recorded)
	Body mass index	Staff measured; calculated by dividing weight (measured with digital scale, in light street clothes and no shoes) in kg by height (measured using with a stadiometer and no shoes) in meters squared; categorized as obese (\geq 30.0), overweight (25.0–29.9), or not obese/overweight (< 25.0) per national guidelines
	Waist circumference	Staff measured; distance around the body at the superior border of the iliac crest; categorized as obese (\geq 30.0),

		overweight (25.0–29.9), or not obese/overweight (< 25.0) per national guidelines
Biometrics (laboratory)	Total cholesterol	Venipuncture following request of 12-hour fast; standard Hutchinson Health medical laboratory blood collection and processing procedures
	HDL cholesterol	
	LDL cholesterol	
	Triglycerides	
	Blood glucose	
	A1c	

REFERENCE

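### The waist circumference row carries the BMI cut-offs, so any waist category built from it is meaningless (low-severity correction)

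*Combined protocol and SAP*

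**What the plan says.** The table of primary and secondary outcome measures has two adjacent rows under staff-measured anthropometrics.

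- **Body mass index.** Weight in kg is divided by "height (measured using with a stadiometer and no shoes) in meters squared; categorized as obese" at 30.0 or more, overweight at 25.0–29.9, "or not obese/overweight (< 25.0) per national guidelines".
- **Waist circumference.** The definition is "distance around the body at the superior border of the iliac crest; categorized as obese", and the rule then continues with the same three ranges and the same closing words as the BMI row.

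Section 4, in the paragraph on measures, lists "Waist Circumference" with no unit and no cut-off. The list stands directly below the sentence that names the secondary outcomes.

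On analysis, section 5 says that the comparison "will examine mean changes in biometric risk factors and the percentage of patients meeting recommended levels for the D5 measures". The paragraph on analyses and power adds: "Mixed regression models will be used to compare D5 outcomes between the two study groups over time". It goes on: "Similar analyses will be conducted on secondary outcomes as well".

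**The concern.** The BMI cut-offs are values in kg/m², whereas waist is a distance. The same numbers cannot be valid for both, and the attribution to national guidelines is repeated along with them. The waist row appears to be a copy of the BMI rule that was never edited.

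This row is the only place in the documents that says how waist is to be categorised. An analyst who codes the variable from it would produce a category that does not vary, or varies little, and so has little or no capacity to show change over the year or a difference between groups. A manuscript is planned (section 12), and a waist category credited to national guidelines but built on BMI numbers would be a reporting error.

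**Working it through.** The plan gives no waist figure to reproduce: no unit, mean, standard deviation or expected change. The check has four steps.

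**1. Is it an artefact of the text extraction?** The waist row has its own measurement description, begins its own categorisation rule, and continues coherently across a page break. It is not a stray fragment of the BMI row. No other section states a waist cut-off.

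**2. Waist recorded in centimetres.** Treating the waist as a circle, 30.0 cm around is 30.0 / π = 9.5 cm across, or 30.0 / 2.54 = 11.8 inches around. No adult aged 40–75 (the eligible range in section 4) has such a waist. Everyone is therefore classed as obese, in both groups and at both visits. This needs no distributional assumption.

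**3. Waist recorded in inches.** The cut-offs convert to 25.0 × 2.54 = 63.5 cm and 30.0 × 2.54 = 76.2 cm. The share classed as obese now depends on the waist distribution, which must be assumed. With a normal distribution of mean m and standard deviation s, in cm:

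share obese = 1 − Φ((76.2 − m) / s)

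Example: m = 100, s = 13 gives (76.2 − 100) / 13 = −1.83, and 1 − Φ(−1.83) = 96.6%.

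| Assumed mean (cm) | SD 10 | SD 13 | SD 16 |
|---|---|---|---|
| 90 | 91.6% | 85.6% | 80.6% |
| 95 | 97.0% | 92.6% | 88.0% |
| 100 | 99.1% | 96.6% | 93.2% |
| 105 | 99.8% | 98.7% | 96.4% |
| 110 | over 99.9% | 99.5% | 98.3% |
| 115 | over 99.9% | 99.9% | 99.2% |

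The range is about 81% to over 99.9%. At the lowest corner, 0.806 × 144 is about 116 of 144 participants classed as obese, leaving about 28 in the other two categories.

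**4. What else uses the rule?**

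- The D5 measures are A1C, blood pressure, tobacco, statin and aspirin. Waist is not among them.
- The BMI row applies its cut-offs to BMI, so it is unaffected.
- The sample size follows from w = 0.25, 85% power, alpha 0.05 and one degree of freedom: (1.960 + 1.036)² / 0.25² = 143.65, rounded up to the stated 144. Waist is not an input.
- Waist kept as a measured value does not use the cut-offs.

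**The case against.** The strongest reply is that this is a copying slip in an appended table with almost no consequence. The primary outcomes do not use waist, and no section describes a between-group comparison of waist categories. The planned analyses (mean changes, percentages meeting D5 levels, mixed models) can all be run without a waist category. That stands, and it is why the point is rated low. It does not remove the point, because the row is a stated classification rule in the outcome table and is wrong as written.

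Three stronger readings are tempting, and the documents support none of them.

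- **That the category is nearly constant whatever the unit.** This is secure only for centimetres. In inches, at an assumed mean of 90 cm, between 8% and 19% of participants would fall outside the obese category.
- **That the planned look at mean changes in biometric risk factors already settles how waist is analysed.** The wording is inconsistent. Section 5 speaks of "coaches documenting lab, biometrics, and medication adjustments in the EHR", which separates biometrics from laboratory values, while the outcome table uses biometrics as its label for laboratory values and puts waist under anthropometrics. A firmer basis is that waist stands in the section 4 list under the secondary outcomes and in the outcome table, so the sentence extending similar analyses to secondary outcomes applies. Even that sentence does not say whether waist enters as a value or as a category.
- **That the correct cut-offs must differ by sex.** The documents refer only to national guidelines, without naming one for waist. They give no basis for specifying the form of the replacement.

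**Conclusion.** The point holds at low severity. The waist row applies kg/m² cut-offs to a length with no unit, and nothing elsewhere corrects it. In centimetres the resulting category is the same for every adult. In inches about 81% to over 99.9% would be classed as obese, a range that rests on assumed normal distributions with means of 90–115 cm and standard deviations of 10–16 cm.

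The harm is confined to any categorical waist result. A reader might infer that the trial's conclusions or its power are at risk. They are not.

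**What to change.** In the outcome-measures table, delete the BMI cut-offs from the waist row and state the unit of measurement. In the analysis paragraph, name waist as a continuous secondary measure under the mixed models already planned for secondary outcomes. This also removes the doubt about what counts as biometric.

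If the sponsor wants waist categories, replace the cut-offs with waist-specific ones taken from the guideline it relies on, and cite that guideline in the row.

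The cost is one table edit, a few words in the analysis paragraph, and the IRB submission that section 10 requires before a protocol change is implemented. Waist is already to be measured at baseline and 12 months, so no new data, visits, participants or methods are needed.
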